9.2 Protecting against sources of bias

Allocation of patients is concealed to prevent selection and information bias. Given the nature of the intervention (RBC transfusion strategy) and its effect on serum hemoglobin measurements, an open-label design is necessary as it is not possible to blind treating practitioners after randomization. As such, we have incorporated independent central blinded outcome assessment and adjudication for all clinical outcomes. Misclassification bias is minimized by applying strict diagnostic criteria for aSAH in the eligibility criteria. Performance bias will be minimized by stratifying patients according to participating sites to ensure equal randomization across sites. We will also track eligible but non-enrolled patients to describe reasons for non-enrolment according to a taxonomy of reasons listed on a study data form. Further, we have attempted to minimize subjectivity in all of the outcome measures by centralizing and blinding the outcome assessor to the treatment allocation and utilizing validated tools for morbidity measures (mRS, FIM and EQ5D) (see Section 6.6). To further reduce risk of bias (performance, attrition, detection and reporting), for the primary outcome, a validated interview/questionnaire administered over the telephone, electronically or by mail will be performed by the assessor (trained and qualified study personnel) blinded to the intervention and who has had no part in the management of the patients.

9.3 Study Monitoring and Auditing

The Trial Coordinator will review the protocol and Data Collection Forms with the investigator and study staff before study initiation at the site initiation visit or the investigator's meeting. A monitor will visit sites as needed throughout the duration of the study to verify the quality of data and to ensure the standards of Good Clinical Practice are being met. (The monitor may be a member of the Study Steering Committee or delegate.) A monitoring plan has been developed and adhered to for the duration of the study (separate document).

The investigator must give the monitor access to relevant hospital or clinical records to confirm their consistency with the Data Collection Form entries. No information in these records about the identity of the patients will leave the study center. Monitoring standards require verification of the presence of informed consent, adherence to the inclusion/exclusion criteria, documentation of all adverse events and outcomes required as per protocol.

The investigator(s)/institution(s) will permit trial-related monitoring, audits, REB review and regulatory inspections(s), providing direct access to source data/documents.

9.4 Loss to follow-up

Previously published papers involving similar patient populations have documented a <1% loss to follow-up.^{72,73} Experience within our own investigative team in traumatic brain injury succeeded in >95% 12-month follow-up employing a similar strategy.⁷⁴ Clinical outcome assessments will occur at 6 and 12 months and, where possible, by telephone, electronic or mailed interview in lieu of follow-up visits with either the patient or their substitute decision maker to facilitate complete follow-up. Public records will be utilized when patients meet minimum lost to follow up, a minimum of 3 unsuccessful attempts to contact in a 3 month timeframe.

10 Ethics, Safety and Privacy

10.1 Ethics

The study protocol will be submitted for approval by the designated Clinical Trials Ontario (CTO) - Board of Record and/or at each participating centers REB. The **intervention and control** arm of the trial are part of usual care in many centers, and thus the research risk to participants is low. Safety considerations are addressed within the protocol, and allow for individualized care where needed.

10.2 Risks to the safety of participants involved in the trial

By virtue of design, we expect that patients in the liberal transfusion strategy arm (100g/L) will receive more red cell transfusions compared to the restrictive arm (80g/L). It is possible that a greater risk of complications associated with transfusion exists due to exposure. However, this was not the case in the only existing small RCT in SAH¹⁷ or other large RCTs in critically ill patients or other patient populations.^{22,72-74} Further, no specific adverse event trends (including acute reactions and infections) associated with either intervention arm have been noted in our current pilot RCT. Complications associated with transfusion will be monitored for, recorded and reviewed by the DSMB as previously described.

10.2.1 Adverse Event Report

Infrequently (less than 1%)	Rarely (less than 0.1%)	Very Rarely (less than 0.001%)

 1. Fever 2. Rash 	
 1. Severe allergic reaction that may be life-threatening 2. Transfusion reaction associated with fevers and with damage to RBCs 3. Injury to the lungs 4. Accumulation of fluid in the lungs 5. Infection 	
 1. HIV (AIDS) 2. Hepatitis C 3. Hepatitis B

10.3 Privacy

Increasingly, medical journals and on-line publishers require that data be stored and made available for secondary review and analysis. For publication purposes participant de-identified study data may be shared for re-analysis.

11 Study Timelines and Milestones

We anticipate a trial duration of 60 months (Table 1). With a run-in start-up period, an enrolment rate of 1.5 patients/center/month, we estimate recruitment to be complete at 40 months. Final follow-up will occur 12 months following leaving 6-8 months for data cleaning, database closure, analysis and result dissemination including publication in major journals.

12 Knowledge Translation (KT) Plan

Integrated KT: Knowledge translation will occur throughout the life of the trial and will begin as study awareness through multidisciplinary presentations at participating centers. We have national reach with bedside clinicians as our study team incorporates critical care, neurosurgical and transfusion medicine specialists at each participating site. Further, the team integrates representatives from key national stakeholder groups including the Heart and Stroke Foundation of Canada ([name], [name]), Canadian Blood Services ([name]), Canadian Critical Care Trials Group (CCCTG – numerous members), and the Canadian Neurocritical Care Society (President – [name]). Lastly, the trial protocol will be registered and published in a peer-reviewed indexed journal.

End-of-Grant KT: The post-trial knowledge translation strategy includes submission of abstracts at national and international conferences, publication of studies in high-impact peer-reviewed open source journals, and incorporation of our findings into clinical guidelines with our partners at Canadian Critical Care Society/Canadian Neurocritical Care Society. Through site presentations, as well as our established national partnerships and collaborations with Canadian Blood Services, the Heart and Stroke Foundation of Canada, and the Canadian Critical Care Trials Group, we will ensure the optimal dissemination of the results to facilitate optimal supply, best practice guidance and bedside uptake respectively.

13 Study team and environment - Strengths and Contributions

APPENDIX:

Figure 1: The SAHaRA Research Program:

A. Current proposed study (circled) in context of research program; B. SAHaRA Trial design

aSAH=aneurysmal subarachnoid hemorrhage, Hb=hemoglobin, mRS=modified Rankin Scale, RBC=red blood cell, RCT=randomized controlled trial

C. SAHaRA Trial outline

[figure not shown]

Table 2: Functional outcome measures:

A. Modified Rankin Scale

Score	Description
0	No symptoms at all
1	No significant disability despite symptoms; able to carry out all ADLs
2	Slight disability; unable to carry out previous activities, but able to look after own affairs with assistance
3	Moderate disability; requiring some help but walks without assistance
4	Moderately severe disability; unable to walk unassisted and unable to look after own bodily needs unassisted
5	Severe disability; bedridden, incontinent and requiring constant nursing care and attention
6	Dead

*modified from Washington University in St. Louis' Internet Stroke Center (www.strokecenter.org)

B. Functional Independence Measure**

I. Assessment Dimensions:		II. Scoring Criteria:		
		Score:	Description:	Category:
1.	Eating	7	Complete independence	No Helper Required
2.	Grooming			
3.	Bathing	6	Modified independence	
4.	Upper body dressing			
5.	Lower body dressing	5	Supervision or setup	Helper - Modified Dependence
6.	Toileting			
7.	Bladder management	4	Minimal contact assistance	
8.	Bowel management			
9.	Bed to chair transfer	3	Moderate assistance	
10.	Toilet transfer			
11.	Shower transfer	2	Maximal assistance	Helper - Complete Dependence
12.	Locomotion			
13.	Stairs	1	Total assistance	
14.	Cognitive comprehension			
15.	Expression	0	Activity does not occur	
16.	Social interaction			
17.	Problem solving			
18.	Memory			

**modified from Rehabilitation Measures Database (www.rehabmeasures.org)

Table 3: Important baseline characteristics and co-interventions to be prospectively logged:

A. Baseline characteristics (from time of enrolment and randomization)

Factor	Variable to capture
Age at enrolment	Age in years
Sex	Male or Female
Ethnicity	As patient identifies
Language	Preferred language
History of CAD, HTN	Present or not
SAH Clinical Severity	WFNS score
SAH radiographic Severity	Modified Fisher Scale Score
Hydrocephalus	Need for EVD
Aneurysm size and location	Size (mm), artery involved
Method aneurysm secured	Clip or coil or not secured
Presence of Delayed Cerebral Ischemia	Delayed cerebral ischemia/radiographic vasospasm *
Presence of cerebral infarct	Cerebral infarct on pre-randomization imaging

CAD=coronary artery disease, EVD=external ventricular drain, HTN=hypertension, SAH=subarachnoid hemorrhage, WFNS=World Federation of Neurosurgeons, *radiographic vasospasm defined as a reduction of cerebral artery diameter on digital subtraction angiography and classified as mild (0-33% reduction), moderate (34-66% reduction) or severe (67-100% reduction) or by transcranial Doppler of the middle or anterior cerebral classified as mild (mean flow velocity of ≥ 120 and < 160 cm/sec AND Lindegaard ratio ≥ 3), moderate (mean flow velocity of ≥ 160 and < 200 cm/sec AND Lindegaard ratio ≥ 3) or severe (mean flow velocity of ≥ 200 cm/sec AND Lindegaard ratio ≥ 3), delayed cerebral ischemia requires a clinical neurologic deterioration (defined as an otherwise unexplained decrease in Glasgow Coma Scale score of ≥ 2 points or new focal neurological deficit for ≥ 2 hours (or ≥ 1 hour and initiation of therapy))

B. Co-Interventions to be prospectively logged

	Co-Intervention	Variable to capture	Operationalization
Delayed Cerebral Ischemia/radiographic vasospasm*	Prophylaxis	Hyperdynamic therapy (prior to diagnosis of DCI)	-use of vasopressors to drive a target MAP>65mmHg
			-use of IV fluid infusions or regular boluses over maintenance
			-use of IV fluids to target specific hematocrit
		Magnesium (prior to diagnosis of DCI)	-use of magnesium IV infusion
	Chemical vasodilators (prior to diagnosis of DCI)	-use of infusion of vasodilator (IV) or any IA use (eg: milrinone, papaverine, CCB etc)	
	Treatment	Hyperdynamic therapy (after diagnosis of DCI)	-same criteria as above
		Magnesium	-same criteria as above
		Mechanical vasodilation	-use of balloon angioplasty or stent
Chemical vasodilation		-use of infusion of vasodilator (IV) or any IA use (eg: milrinone, papaverine, CCB etc).	
Definitive Aneurysm Management (if completed post randomization)	Clip vs coil		
	Time to clip or coil		
Blood pressure management	-daily use of vasopressor	-used or not	
	-highest daily target MAP		
Fever/temperature regulation	-fever	-daily highest temperature	

MAP=mean arterial pressure, IV=intravenous, IA=intra-arterial, CCB=calcium channel blocker, *radiographic vasospasm defined as a reduction of cerebral artery diameter on digital subtraction angiography and classified as mild (0-33% reduction), moderate (34-66% reduction) or severe (67-100% reduction) or by transcranial Doppler with a mean middle or anterior cerebral artery flow velocity of >200cm/s or an increase of >50cm/s/24h on repeated measures and a Lindegaard ratio of ≥ 3 , delayed cerebral ischemia requires a clinical neurologic deterioration (defined as an otherwise unexplained decrease in Glasgow Coma Scale score of ≥ 2 points or new focal neurological deficit for ≥ 2 hours (or ≥ 1 hour and initiation of therapy))

Table 4: Schedule of assessments

Assessment:	Baseline:	Prospective – Daily	Hospital Discharge	6 months	12 months
Eligibility Criteria	X				
Recruitment	X				
Informed Consent	X				
Randomization	X				
Baseline Demographics	X				
Medical History	X				
Physical Exam including BP, O2 sat, GCS	X	X	X		
Baseline labs	X				
aSAH clinical grade	X				
Neuro imaging (U/S, CT, MRI, Angio...)	X				
DCI monitoring (CTA, U/S, angio...) and management	X	X	X		
Laboratory results		X	X		
Transfusion Requirements		X	X		
Co-intervention Log		X	X		
Adherence to treatment		X	X		
AE Review		X	X		
Neurologic outcome (mRS)			X	X	X
Functional Independence Measure (FIM)					X
EuroQOL Quality of Life Scale (EQ5D)					X


CBS – Canadian Blood Services

CIHR – Canadian Institutes of Health Research

CT - Computed Tomography

DCI – delayed cerebral ischemia

DSMB - Data Safety Monitoring Board

EQ-5D- 5L - EuroQOL Quality of Life Scale 5-Dimension 5-Level

eSAE - expected Serious Adverse Events

FIM - Functional Independence Measure

HAU - high-acuity unit

Hb - hemoglobin

MCID - minimal clinically important difference

mFS – modified Fisher Scale

mRS – modified Rankin Scale

RCT – randomized controlled trial

SAP – statistical analytic plan

uSAE -unexpected Serious Adverse Events

VAS – visual analogue scale

WFNS – World Federation of Neurological Surgeons

Section 1: Introduction

1.1 Background and Rationale

Aneurysmal subarachnoid hemorrhage (aSAH) is an important disease with devastating outcomes. Morbidity can be profound, with less than one third of survivors achieving a full functional recovery.¹ Anemia is common in these patients and is a potential critical factor affecting secondary injury, an often-protracted process.²⁻⁶ Despite physiologic evidence⁷ and management guidelines^{8,9} that support maintaining a higher hemoglobin level in patients with aSAH, stated current practice from surveys¹⁰ and from our multi-center cohort study¹¹ favors a more restrictive approach to transfusion in a similar fashion to other critical care patients^{12,13}. The clinical importance of varied transfusion thresholds in aSAH has never been studied in a large and rigorous randomized trial. In collaboration with the Canadian Critical Care Trials Group, we are conducting an open-label single blind RCT in adult patients with aSAH to examine the effect of a liberal compared to restrictive RBC transfusion strategy (Hb trigger $\leq 100\text{g/L}$ vs $\leq 80\text{g/L}$ respectively) on 12-month functional neurologic outcome.

1.2 Objectives

Our primary objective:

To evaluate the effect of a liberal (Hb trigger $\leq 100\text{g/L}$) versus a restrictive (Hb trigger $\leq 80\text{g/L}$) RBC transfusion strategy in acute aSAH patients with anemia ($\text{Hb} \leq 100\text{g/L}$) on patient-oriented functional neurologic outcome at 12 months.

Our secondary objectives:

To evaluate the effect of a liberal versus a restrictive RBC transfusion strategy on: a) 12-month overall function; b) quality of life at 12 months; c) mortality; d) delayed cerebral ischemia and radiographic vasospasm and e) clinically relevant stroke at hospital discharge on routine brain imaging.

Our tertiary objectives:

To evaluate the effect of a liberal versus a restrictive RBC transfusion strategy on lowest daily hemoglobin levels, RBC transfusions, expected and transfusion-related adverse events, mechanical ventilation and ICU and hospital length of stay.

Section 2: Study Methods

2.1 Trial Design

SAHaRA is a multicenter pragmatic randomized trial in patients with aSAH that compares the effect of a liberal to a restrictive RBC transfusion strategy on the combined rate of death and severe disability at 12 months. Our PROBE (prospective, open-label, blinded endpoint) approach has been informed by and tested in our CIHR/CBS-funded pilot RCT.¹⁴

Trial interventions

Eligible patients are randomized to either a restrictive or a liberal RBC transfusion strategy. Hemoglobin is checked at least daily while on protocol up to and including Day 10 post aSAH or while in an ICU/HAU (high-acuity unit), and then at the discretion of the primary clinical team.

Restrictive RBC Transfusion Strategy: For patients randomized to this group, an RBC transfusion is permitted once a hemoglobin level of ≤ 80 g/L is observed over the first 21 days following aSAH. RBC transfusion below the threshold is not mandatory, rather “usual care” prevails, with the decision and timing of transfusion left to the discretion of the treating team.

Liberal RBC Transfusion Strategy: An RBC transfusion is triggered by a hemoglobin level of ≤ 100 g/L over the first 21 days in hospital following aSAH. Transfusion in this arm is mandatory.

Both Groups: All RBC transfusion orders are single unit unless the patient has active blood loss associated with hemodynamic instability (see section 9.1 of the protocol – see Appendix). In stable non-bleeding patients, a second unit of RBCs is given if a measured post-transfusion hemoglobin level remains below the patient’s assigned threshold. Protocol adherence and violations are discussed in section 9.1 of the protocol (see Appendix).

Duration of the intervention

The allocated transfusion strategy is applied from the time of randomization to 21 days after the original bleed, death or hospital discharge, whichever comes first. The first 21 days following aSAH represent the period of greatest vulnerability to the direct consequences of aSAH, and the sequelae, including DCI, that follow.

2.2 Randomization

A web-based central computer-generated randomization, stratified by centre, was undertaken from the sponsoring centre. Upon meeting the randomization criteria, patients were randomized in a 1:1 manner to either restrictive or liberal RBC transfusion strategy groups, stratified by site. Variable random blocks of 4 and 6 was used. For patients randomized to the restrictive group, an RBC transfusion is permitted once a hemoglobin level of ≤ 80 g/L is observed over the first 21 days following aSAH. For patients randomized to the liberal group, an RBC transfusion is permitted once a hemoglobin level of ≤ 100 g/L is observed over the first 21 days in hospital following aSAH. The trial is an open-label blinded-endpoint randomized control trial. All outcomes are ascertained by an assessor (trained and qualified study personnel) blinded to the intervention and who has had no part in the management of the patients.

2.3 Sample Size

Based on our foundation work and previously published literature, we anticipate unfavourable neurologic outcome (mRS score of ≥ 4) at 12 months in 40% of the restrictive arm group.^{8,11,15,16} Previous studies involving SAH patient populations have supported a minimal clinically important difference (MCID) of a 25% relative improvement in poor neurologic outcome.¹⁷ Therefore, to demonstrate a 25% relative improvement in event rate (i.e., from 40% to 30%), a total sample size of 740 patients (test of independent proportions¹⁸) is necessary given 80% power, a type I error of 5% and a conservative 3% loss to follow-up factor.

2.4 Interim Statistical analyses and stopping guidance

One full interim, blinded analysis after the first 370 patients randomized was reviewed by the Data Safety Monitoring Board (DSMB) guided by a pre-specified charter. The data was then

tested for efficacy using the Haybittle-Peto criterion ($p < 0.001$).¹⁹ At this point there was not enough evidence to stop the trial for efficacy. Due to using the Haybittle-Peto criterion the final analysis will be conducted at $p < 0.05$. Regular (biannual) reports of patient recruitment, intervention fidelity and adverse event reporting were provided to and reviewed by the DSMB.

2.5 Timing of final analysis

The trial enrolment is complete. Participant follow up continues, with the last 12-month follow-up assessment completed by end of July 2024. The data will be cleaned, verified, and locked. The publication of this SAP will occur prior to the database lock. Final analysis will commence once the final lock has been confirmed by the principal investigator. Unblinding will only occur once the primary and secondary analyses are complete.

2.6 Timing of outcome assessment

Primary outcome:

- a) Modified Rankin Scale (mRS) score [12 months]

Secondary outcome:

- a) Functional Independence Measure (FIM) [12 months]
- b) EuroQOL Quality of Life Scale 5-Dimension 5-Level (EQ-5D-5L) and visual analogue scale (VAS) [12 months]
- c) Mortality [in-hospital]
- d) Delayed Cerebral Ischemia and Radiographic Vasospasm [over the first 21 days in hospital]
- e) New cerebral infarction [in-hospital]

Tertiary outcome:

- a) Lowest daily hemoglobin level [over the first 21 days in hospital]
- b) Proportion of patients who have an RBC Transfusion [over the first 21 days in hospital]
- c) Expected and transfusion-related adverse events [over the first 28 days in hospital]
- d) Need for and duration of mechanical ventilation [in-hospital]
- e) Length of stay [in-hospital]

Section 3: Statistical Principles

3.1 Confidence Intervals and P-values

The statistical uncertainty of all estimates will be expressed as two-sided 95% confidence intervals. Therefore, the analyses for an unfavorable neurologic outcome will be tested at a 0.05 level of significance. A p-value will only be reported for the primary outcome.

3.2 Adherence and protocol deviations

The study adherence is measured in 2 domains:

1) Adherence to allocated transfusion threshold: This occurred if an RBC transfusion is given only in response to the transfusion threshold being crossed with the last hemoglobin measure prior to transfusion being below the appropriate threshold. *Non-adherence* will be considered to have occurred if a) an RBC transfusion occurs before a transfusion threshold is crossed; or b) in the liberal arm, a transfusion is not given following a threshold crossing. Non-adherence will be

considered a *deviation* if: 1) the early transfusion occurs within 5 g/L above the allocated threshold (e.g., ≤ 105 g/L for the liberal arm or ≤ 85 g/L for the restrictive arm) or, 2) in the liberal arm, an RBC transfusion does not occur for a hemoglobin measure up to 5 g/L below the threshold (i.e.: a transfusion does not occur for a hemoglobin of 95-100 g/L). All other threshold event non-adherences will be considered a protocol violation. Details on non-adherence (date and hemoglobin level prior to transfusion) and reasons for non-adherence will be recorded. In the event of an active blood loss associated with hemodynamic instability, as defined by the treating team, standard resuscitation practices prevail (including blood product administration). Transfusion under this circumstance would not be a protocol violation. The allocated transfusion strategy will resume when hemodynamic stability is achieved and it is the opinion of the treating team that active bleeding has stopped. Transfusion outside of hemoglobin thresholds for symptomatic anemia (as assessed by the bedside team) will be recorded, but not considered a protocol violation.

2) Adherence to transfusion protocol (timely transfusion): We endeavor not to exceed 6 hours from transfusion threshold event to transfusion initiation, in keeping with revascularization time performance measures in stroke literature.^{20,21} Transfusion protocol adherence is thus defined as an RBC transfusion initiated within 6 hours of threshold crossing, or Randomization. *Non-adherence* will be considered to have occurred if there is a delay of more than six hours between transfusion threshold event and transfusion initiation. Transfusions occurring more than 6 hours but within 24 hours will be considered a deviation. A protocol violation is a transfusion initiated greater than 24 hours from the threshold event. We documented reasons for non-adherence in the study case report form.

We will assess adherence by evaluating the number of:

- All protocol violations (per patient).
 - All transfusion threshold violations (per patient).
 - All time to transfusion violations (per patient).

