1) **Adherence to allocated transfusion threshold:** This will have occurred if: 1) a RBC transfusion is given in response to the transfusion threshold being crossed; or 2) a repeated hemoglobin value no longer crosses the threshold ending the transfusion threshold event. **Non-adherence** will be considered to have occurred if a) an RBC transfusion occurs before a transfusion threshold is crossed; or b) in the liberal arm, a transfusion is not given following a threshold crossing. Non-adherence will be considered a *deviation* if: 1) the early transfusion occurs within 5 g/L above the allocated threshold (e.g. ≤ 105 g/L for the liberal arm or ≤ 85 g/L for the restrictive arm) or, 2) in the liberal arm, an RBC transfusion does not occur for a hemoglobin measure up to 5 g/L below the threshold (i.e.: a transfusion does not occur for a Hb of 95-100 g/L). All other threshold event non-adherences will be considered a protocol violation. Details on non-adherence (date and hemoglobin level prior to transfusion) and reasons for non-adherence will be recorded. In the Pilot RCT we had 93% compliance with RBC transfusion according to allocation at the mid-point interim analysis. In the event of an active blood loss associated with hemodynamic instability, as defined by the treating team, standard resuscitation practices

prevail (including blood product administration). Transfusion under this circumstance would not be a protocol violation. The allocated transfusion strategy will resume when hemodynamic stability is achieved and it is the opinion of the treating team that active bleeding has stopped. Transfusion outside of hemoglobin thresholds for symptomatic anemia will be recorded, but not considered a protocol violation.

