3.3 Analysis populations

Intention to Treat population: this population includes all aSAH patients randomized except those who were a post-randomization exclusion, withdrew consent, or were lost to follow up.

Per Protocol Population: this population is the intention to treat population except those who had a protocol violation (as defined in 3.2).

The primary analysis of all outcomes will be conducted on the Intention to Treat population. A secondary, sensitivity analysis, on the Per Protocol population will also be conducted and reported separately, accompanied by a description of the population characteristics, in the supplement.

Section 4 – Trial Population

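### SAP 3.2 omits the Protocol's repeat-hemoglobin route to adherence, so its literal wording drops from the per-protocol set some untransfused liberal-arm patients whom Protocol 9.1 can be read to call adherent

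*SAP*

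**What the plan says.** Protocol 9.1 gives two ways to adhere to the allocated threshold. One is a transfusion in response to a crossing. The other needs no transfusion: "a repeated hemoglobin value no longer crosses the threshold ending the transfusion threshold event".

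SAP 3.2 rewrites that definition. It keeps the transfusion route ("This occurred if an RBC transfusion is given only in response to the transfusion threshold being crossed") and adds a condition, "with the last hemoglobin measure prior to transfusion being below the appropriate threshold". The repeat-hemoglobin route does not appear.

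The rest of the rule is essentially the same in both documents. Clause (b) makes it non-adherence when "in the liberal arm, a transfusion is not given following a threshold crossing". This is only a deviation if "in the liberal arm, an RBC transfusion does not occur for a hemoglobin measure up to 5 g/L below the threshold", that is, at 95 to 100 g/L. Then: "All other threshold event non-adherences will be considered a protocol violation".

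SAP 3.3 defines the per-protocol population from these classes: "this population is the intention to treat population except those who had a protocol violation (as defined in 3.2"). Deviations do not exclude; violations do. SAP 2.1 adds for the liberal arm: "Transfusion in this arm is mandatory". SAP 2.1 also refers the reader to Protocol 9.1 for adherence and violations.

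**The concern.** Clause (b) was written next to a sentence saying that a non-crossing repeat closes the event. In the SAP it stands without that sentence. A liberal-arm patient whose hemoglobin recovers above 100 g/L before any transfusion can therefore be a violator in the SAP and adherent in the Protocol.

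The per-protocol analysis is one of the four sensitivity analyses of the primary outcome in SAP 5.2. SAP 3.2 also plans per-patient counts of threshold violations. Two analysts working from these documents could build different per-protocol sets and report different violation counts. Because clause (b) applies only to the liberal arm, the extra exclusions would fall in that arm alone, in an open-label trial.

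**Working it through.** The point rests on no numerical figure in the plan, so the check is a classification. The inputs are the adherence rules of Protocol 9.1 and SAP 3.2 and the exclusion rule of SAP 3.3. The cases are untransfused liberal-arm patients (trigger at or below 100 g/L) without active bleeding or symptomatic anemia, for which both documents make exceptions. Protocol 9.1 gets two columns because its repeat-hemoglobin sentence and its clause (b) can both apply to one patient.

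| First Hb (g/L) | Repeat Hb (g/L) | Protocol 9.1, repeat sentence governs | Protocol 9.1, clause (b) governs | SAP 3.2, literal | SAP per-protocol set |
|---|---|---|---|---|---|
| 94 | none | violation | violation | violation | out |
| 94 | 99 | violation | violation | violation | out |
| 94 | 102 | adherent | violation | violation | out |
| 98 | none or 99 | deviation | deviation | deviation | in |
| 98 | 102 | adherent | deviation | deviation | in |

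Only the third row changes membership of the per-protocol set. It needs a first value below 95, a repeat above 100 and no transfusion. At 95 to 100 the SAP label differs from the Protocol's first reading, but the patient stays in.

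The SAP rule is also awkward on its own terms. After a repeat above 100, not transfusing meets clause (b), while transfusing fails the last-hemoglobin condition. Outside the stated exceptions, neither course is adherent if the last value governs. That suggests a drafting slip, but does not prove one.

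As to size, the documents do not say how often the third row occurs. For illustration only, assume that a fraction x of the liberal arm is removed, that those removed have event risk r, and that nobody is removed from the restrictive arm. With the planning risks of SAP 2.3 (40% restrictive, 30% liberal), the remaining liberal-arm risk is (0.30 − x·r)/(1 − x), and the risk ratio is that value divided by 0.40.

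- x = 5%, r = 15%: (0.30 − 0.0075)/0.95 = 0.308; risk ratio 0.77.
- x = 5%, r = 45%: (0.30 − 0.0225)/0.95 = 0.292; risk ratio 0.73.
- x = 10%, r = 15%: (0.30 − 0.015)/0.90 = 0.317; risk ratio 0.79.
- x = 10%, r = 45%: (0.30 − 0.045)/0.90 = 0.283; risk ratio 0.71.
- r = 30%, any x: risk ratio stays at 0.75.

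The shift can go either way. Both x and r are assumptions.

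A lesser point lies in the timing rule, which is the same in both documents. A transfusion started more than 24 hours after the threshold event is a violation in either arm. Yet SAP 2.1 and Protocol 6.3 leave to the clinicians whether and when to transfuse in the restrictive arm. With the clock at the first crossing, a restrictive-arm patient at 78 g/L transfused at 30 hours is excluded, while one never transfused is kept. The liberal arm shows the same oddity: at 97 g/L, transfusion at 30 hours excludes, and no transfusion is only a deviation. Neither document defines when the event starts for serial hemoglobin values.

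**The case against.** The strongest reply is that Protocol 9.1 contains the same clause (b), the same 95 to 100 g/L band and the same residual violation clause. The patient at 94 then 102 therefore meets two opposed sentences within the Protocol. A reader might infer that the Protocol plainly calls this patient adherent and that the SAP plainly contradicts it. The documents do not support that: the contrast needs the repeat-hemoglobin sentence to take precedence. I think that is the natural reading, since the sentence says that the event has ended, but the Protocol does not state the precedence.

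Second, the SAP need not be read literally. It refers to Protocol 9.1 for adherence, its residual clause speaks of threshold events, and only the Protocol says when such an event ends. This stands in part. The cross-reference is general, however, whereas the per-protocol definition points to SAP 3.2. If both texts apply, membership of the set is ambiguous.

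Third, the omission may be deliberate, since the SAP rewrote the definition and calls liberal-arm transfusion mandatory. That is possible, but the SAP neither says so nor gives a reason.

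A reader might also infer that the same patient, if transfused after the repeat of 102, would always be kept. That does not follow. Hemoglobin need be checked only daily, so the transfusion could come more than 24 hours after the first crossing and be a timing violation if the clock starts there. With a repeat above 105, it would be a threshold violation if the last value governs.

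**Conclusion.** The point holds as a minor inconsistency in the definition of a supplementary analysis set. On a literal reading, SAP 3.2 and 3.3 exclude untransfused liberal-arm patients with a first hemoglobin below 95 g/L and a repeat above 100 g/L. Protocol 9.1 counts them as adherent if its repeat-hemoglobin sentence prevails over its clause (b). The omission itself is certain; the exclusion rests on the literal reading.

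It affects the per-protocol sensitivity analysis and the violation counts. A reader might infer that the trial's main result is at risk or that the analysis is tilted toward one strategy. Neither is supported: the primary analysis uses the intention-to-treat population, and the direction of any per-protocol bias depends on the unknown risk of those removed.

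Nor do the pilot figures in Protocol 5.3 bound the problem. They are counted per transfusion episode, so a crossing that led to no transfusion may not be among them.

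The 24-hour point is separate and lesser. The conflict with clinician discretion is confined to the restrictive arm, but the anomaly that a late transfusion excludes and none does not arises in both arms.

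**What to change.** Before database lock:

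1. Reconcile SAP 3.2 with Protocol 9.1 by carrying the repeat-hemoglobin route into the adherence definition used for the per-protocol set, and say that it takes precedence over clause (b). Alternatively, state that the stricter rule is intended and why.
2. Tabulate per-protocol exclusions by arm and reason. This extends the per-patient violation counts that SAP 3.2 already plans.
3. As a lesser item, reconcile the 24-hour rule (SAP 3.2, Protocol 9.1) with the restrictive-arm provisions of SAP 2.1 and Protocol 6.3, and define when a threshold event starts for serial values. Which passage governs is for the sponsor to settle.

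The cost is a few lines of SAP text and one supplementary table. Reclassification should be possible from hemoglobin values, dates and reasons for non-adherence already collected. If only the lowest value of a day was entered, a same-day repeat may have to be sought in source records for the few patients concerned. Enrolment is complete, so patient care does not change.
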